### Secondary Endpoints:

- Incidence and severity of adverse events from baseline through post-op day 45
- Degree of inflammation (AC cell count)
- Resolution of inflammation as defined as either 0

---

or 0.5 or less cell on follow up post op exams

- Resolution of pain using the Face, Legs, Activity, Cry, Consolability (FLACC) Behavioral Pain rating Scale. Ratio of Intraocular pressure increase with insert
- % of patients with rebound inflammation from baseline through post-op care
- % of patients that were given supplementary prednisolone drops and the number of drops needed in these patients
- Mean change in BCVA from baseline over time using either ETDRS or HOTV chart testing depending on age
- Primary caregiver's ability to adhere to treatment plan as prescribed and therapeutic preferences measured with primary caregiver satisfaction survey

## 1. INTRODUCTION AND RATIONALE

Corticosteroids are routinely prescribed for the post-operative management of inflammation and pain following retinal surgery. Persistent ocular inflammation can increase the risk of ocular complications such as increased intraocular pressure (IOP), ocular pain, and reduced visual outcomes, where as untreated pain can affect overall patient satisfaction. Despite the widespread use of topical eyedrops, this means of treatment is often associated with poor patient compliance. This issue is further complicated in pediatric patients, who often dislike eye drops leading to difficulty with administration in the post-op period by parents. Largely across preparations, there is poor bioavailability from eyedrops with less than 5% of the applied dose of topical preparations predicated to reach the intraocular tissues.

To optimize the delivery of a corticosteroid after ocular surgery, a sustained-release intracanalicular dexamethasone insert (DEXTENZA, Ocular Therapeutix, Inc) has been approved by the FDA to treat ocular pain and to control inflammation after ocular surgery.

## 2. STUDY OBJECTIVES

### 2.1 Primary Objective

To determine if pediatric retinal patients would benefit from the placement of the 0.4 mg sustained release Dexamethasone intracanalicular insert (DEXTENZA) in the inferonasal lacrimal system during surgery in the surgical/treated eye compared to topical ocular drop therapy to manage post-operative pain (measured with Face, Legs, Activity, Cry Consolability (FLACC) Behavioral Pain Rating Scale). Pain will be measured at each visit with final outcome determined by the FLACC Behavioral Pain Rating Scalescore on day 45.

### 2.2 Secondary Objectives

- Incidence and severity of adverse events from baseline through post-op day 45
- Degree of inflammation (AC cell count)
- Resolution of inflammation as defined as either 0 or 0.5 or less cell on follow up post op exams
- Resolution of pain using the FLACC Behavioral Pain Rating Scale
- Ratio of Intraocular pressure increase with insert
- % of patients with rebound inflammation from baseline through post-op care
- % of patients that were given supplementary prednisolone drops and the number of drops needed in these patients

- Mean change in BCVA from baseline over time using either ETDRS or HOTV chart testing depending on age
- Primary caregiver's ability to adhere to treatment plan as prescribed and therapeutic preferences measured with primary caregiver satisfaction survey

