**Table 1 Treatment Arm Schedule of Events**

Study Procedure	Screening/ Baseline	Surgical Visit Day 0	Day 1	Day 7	Day 28	Day 45
Visit	VISIT 1	VISIT 2	VISIT 3	VISIT 4	VISIT 5	VISIT 6
Windows for Visits	(Day -30 to 0)		+/- 3 days	+/- 3 days	+/- 3 days	+/- 3 days
Inclusion/Exclusion	X					
Informed Consent	X					
Demographics	X					
Medical History and Concurrent Illnesses	X					
Concomitant Medications	X					
Pregnancy testing as indicated/appropriate		X				
Subject reported AEs prior to or after surgery	X	X	X	X	X	X
Randomization with subsequent intracanalicular dexamethasone insert placement		X				
Easy of insertion		X				
If dilator was used		X				
Document administration of prescribed medications			X	X	X	X
Ocular Pain Assessment (FLACC)	X		X	X	X	X
Distance VA testing	X		X	X	X	X
BCVA (ETDRS at 4m)	X		X	X	X	X
Anterior chamber cell count	X		X	X	X	X

Study Procedure	Screening/ Baseline	Surgical Visit Day 0	Day 1	Day 7	Day 28	Day 45
Visit	VISIT 1	VISIT 2	VISIT 3	VISIT 4	VISIT 5	VISIT 6
Windows for Visits	(Day -30 to 0)		+/- 3 days	+/- 3 days	+/- 3 days	+/- 3 days
Anterior chamber cell flare	X		X	X	X	X
Punctum examination	X	X	X	X	X	X
Insert Visualization and ease of visualization score			X	X	X	X
Intraocular Pressure	X		X	X	X	X
Ophthalmic Examination (dilated fundus exam)	X		X	X	X	X
Satisfaction Survey						X

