## **5.3 Rescue Treatment**

Rescue treatment will be left to the discretion of the surgeon. Rescue treatment includes but is not limited to topical NSAID, oral and topical steroids. Rescue treatment will be adequately documented to include the dosage needed.

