#### **8.1.2 Safety**

The safety reports will be summarized.

Serious adverse events will be presented overall. Severity and relationship to study drug will be provided.

Events of special interest will be presented overall and summarized by participant characteristics.

Prior and concomitant medications will be summarized by World Health Organization (WHO) drug class.

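### The only rescue-type endpoint counts supplementary prednisolone drops, although section 5.3 allows a wider, open list of rescue treatments, and non-prescribed drugs have no post-operative recording row

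*Combined protocol and SAP*

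**What the plan says.** **Endpoint.** Section 2.2, repeated in the Synopsis under Secondary Endpoints, asks for the percentage "of patients that were given supplementary prednisolone drops and the number of drops needed in these patients". No other endpoint concerns rescue.

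**Permitted rescue.** Section 5.3 states: "Rescue treatment will be left to the discretion of the surgeon". It then gives an open list: "Rescue treatment includes but is not limited to topical NSAID, oral and topical steroids". It closes with a recording duty: "Rescue treatment will be adequately documented to include the dosage needed".

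**Resolution.** Section 2.2 defines resolution of inflammation by anterior chamber cell grade alone (0.5 or lower). Pain appears as "Resolution of pain using the FLACC Behavioral Pain Rating Scale", with no cut-off. Neither definition mentions rescue, and section 8 has no rule for outcomes observed after it.

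**Recording.** Tables 1 and 2 mark "Document administration of prescribed medications" at Days 1, 7, 28 and 45 in both arms. The matching item in section 5.2.1 asks whether medication was used and how many drops. The row "Concomitant Medications" is marked at screening only in both tables, and section 5.2.1 lists it only under Visit 1. Section 8.1.2 nevertheless plans: "Prior and concomitant medications will be summarized by World Health Organization (WHO) drug class".

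**The concern.** The trial is open-label, and the surgeon chooses whether to rescue and with what. If the reported rescue figure covers one product while several are allowed, it depends on the choice of drug as well as on the need for rescue. Two arms with the same need could show different percentages simply because different drugs were used.

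The resolution endpoints raise a related problem. They are silent on rescue, so a child who needed extra treatment and then settled can appear as a resolved case in the assigned arm. With an incomplete rescue percentage beside that figure, a reader cannot tell how much resolution was reached without help.

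An analgesic given at home before a visit could lower that day's FLACC score. FLACC is also the scale for the primary endpoint, and the schedule has no post-operative place to record such a drug unless it was prescribed.

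Section 8.1 says the study is a feasibility study and is not powered. Its descriptive percentages are therefore its main product, and they need to describe what happened.

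**Working it through.** **1. The plan's own figure.** The only figure that can be checked is the allocation: 2 procedure groups × (10 insert + 5 control) = 30, that is 20 insert and 10 control. This agrees with sections 4.1 and 8.1. The plan gives no rescue rate, effect size or error rate, so there is no power figure to reproduce.

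**2. Permitted rescue against counted rescue.**

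| Rescue given (section 5.3) | In the section 2.2 percentage? | Recorded after surgery? |
|---|---|---|
| Supplementary prednisolone drops | Yes | Yes |
| Another topical steroid | No | Yes, if prescribed |
| Topical NSAID | No | Yes, if prescribed |
| Oral steroid | No | Yes, if prescribed, though the visit item asks for drops |
| Other drug under the open list, prescribed | No | Yes |
| Over-the-counter analgesic | No | No row; covered by section 5.3 only if treated as rescue |

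The count is narrower than the permission. For prescribed drugs, the data to widen it should already exist.

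**3. How far the percentage can fall short.** Let r be the true proportion rescued and s the share of rescued children who receive no prednisolone drops. Then

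counted rescue = r × (1 − s).

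Both r and s are assumptions, because the documents give neither.

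| r | s = 25% | s = 50% | s = 75% |
|---|---|---|---|
| 20% | 15% | 10% | 5% |
| 40% | 30% | 20% | 10% |

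In the insert arm, r = 20% and s = 50% means 20 × 0.20 × 0.50 = 2 rescued children left out. At r = 40% and s = 75% it is 20 × 0.40 × 0.75 = 6.

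**4. Effect of one child.** Reclassifying one child, whether for rescue or for resolution, moves a rate by:

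- overall: 1/20 = 5 points (insert) and 1/10 = 10 points (control);
- within a procedure group: 1/10 = 10 points (insert) and 1/5 = 20 points (control).

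Section 8.1 plans both the overall and the by-procedure presentation, so both sets apply.

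**5. The concomitant-medication summary.** Section 8.1.2 plans a summary of prior and concomitant medications, but the row that would supply it is marked at screening only. After surgery, the only sources are the prescribed-medication item and the rescue record, and neither asks for non-prescribed drugs.

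**The case against.** Several stronger readings are tempting, and the documents do not support them.

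- **A reader might infer that rescue with other drugs goes unrecorded.** It does not. Section 5.3 requires documentation with dosage, and prescribed medications are recorded at every post-operative visit in both arms. Only non-prescribed drugs lack a row, and the drops wording fits oral drugs poorly. Section 5.3 does not name analgesics; they fall only under its open wording.
- **A reader might infer that these children are classified as not rescued and as resolved.** The endpoint is labelled as supplementary prednisolone use, so it says nothing formal about other rescue; a summary of any rescue is simply absent. A rescued child is resolved only if the cell grade or FLACC score qualifies, and pain resolution has no stated cut-off.
- **A reader might infer that failure is understated mostly in the insert arm, because it has no background drops.** No rescue rate or mix is given. The opposite is equally plausible: controls already on prednisolone may be rescued with something else, so the count could miss more there.
- **A reader might infer that the count is meaningless in controls because all 10 take prednisolone.** The word supplementary already points beyond the assigned taper, which section 4.1 sets out by day. It needs an operational definition, no more.

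There is also a fair objection to treating rescue as non-resolution. Analysing outcomes regardless of rescue is a legitimate estimand. Making rescue equal failure in the main analysis would tie FLACC, which Appendix 10.3 assigns to masked personnel, to an unmasked surgeon's decision. That objection stands, and it is why the rescue-as-failure count belongs in a supplementary table. The stakes are limited too: the study is descriptive, and no test or sample size changes.

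The mismatch between the endpoint and section 5.3 survives all of this, as do the lack of a rule for outcomes after rescue and the summary that has no post-operative source for non-prescribed drugs.

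**Conclusion.** The concern holds as one of definition, with a smaller recording gap. Followed as written, the plan reports a percentage that leaves out rescue it expressly permits, and a child so rescued can still appear as resolved. Non-prescribed drugs are not collected after surgery, so the planned concomitant-medication summary would be incomplete for that period.

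The size cannot be estimated from the documents. The table of r and s rests wholly on assumed values and shows the range only. The figures of 5 and 10 points per child overall, and 10 and 20 within a procedure group, follow from the planned allocation and assume that all 30 children are enrolled and assessed. No direction by arm can be claimed. The effect is on interpretation of the descriptive results. The change is worth making because it is cheap and most of the data should already be collected.

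**What to change.** 1. **Restate the endpoint** in section 2.2 and the Synopsis as the percentage of patients given any section 5.3 rescue treatment beyond the assigned regimen, by class and by arm. Keep supplementary prednisolone drops as one component, defined in controls as drops beyond the scheduled taper. Tying the count to section 5.3 rescue keeps out drugs taken for unrelated conditions, which section 4.3 allows.
2. **Extend the concomitant-medication row** in Tables 1 and 2 and the list in section 5.2.1 to the post-operative visits (Visits 3 to 6), including any analgesic taken before that day's FLACC. This also gives the section 8.1.2 summary its post-operative data.
3. **State the handling of rescue in section 8.** Report resolution of pain and of inflammation as observed, and add a supplementary table that counts a child as not resolved at and after first rescue.

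The cost is one case report form row at existing visits and one extra table. The reported rescue rate may be higher than under the present definition. The supplementary table depends on an unmasked surgeon's decision and should carry a note saying so. Only counting and recording change; when and how to rescue stays as the protocol has it.

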### **4. SELECTION, WITHDRAWAL, AND REPLACEMENT OF PATIENTS**

#### **4.1 Study Population**

The study aims to enroll 30 pediatric patients undergoing routine retinal surgery or laser treatment under anesthesia. Patients in each treatment group (surgery or laser) will be randomized 2:1 at the time of surgery/laser to receive either:

- 3) Treatment Arm: Dextenza insert intraoperatively for perioperative ocular inflammation and pain. These patients will not be prescribed topical steroid drops post-operatively, or
- 4) Control Arm: Prednisolone forte 1% steroid drop taper for 28 days post-operatively to treat perioperative ocular inflammation and pain; drops four times per day (QID) on days 0-7, three times per day (TID) on days 7-14, twice per day (BID) on days 14-21 and once per day (QD) on days 21-28.

Each treatment group (surgery or laser) will include 15 patients total, 10 receiving Dextenza and 5 receiving the control drug. Drops for dilation and antibiotic coverage will be used as clinically indicated in all groups throughout the study period. Follow up will occur at post-op day 1, 7, 28/30 and 45 (+/- three days for all post-operative timepoints).

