## **8. STATISTICAL CONSIDERATIONS**

### **8.1 Sample Size Considerations and Analysis Plan**

This is a feasibility study and the sample size of 30 is not designed to provide power to determine any differences between arms.

Analysis results will be presented by study drug vs. standard of care topical drops overall and by surgical procedure group.

Descriptive statistics such as number of observations, mean, median, standard deviation, minimum and maximum will be presented by treatment arms for continuous variables (such as age, weight, etc.). Other descriptive statistics such as counts, proportions, and/or percentages will be presented by group to summarize discrete variables (such as race, sex, etc.).

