### Instructions

The HOTV matching method will determine the visual acuity more accurately and at a younger age than many other tests. It is accurate because four actual optotypes are used as matching objects. Children will learn to match them as readily as squares, triangles, etc. Because they are the same optotypes used by eye care professionals, they give meaningful results. Frequently children younger than 3 years and many handicapped can be tested.

The first step is to familiarize the child with the four optotypes (HOTV). This is best done by holding one of the flash cards a few feet in front of the child and have the child match the same optotype on the response panel. Several children can be familiarized at the same time. This step usually requires only a minute or two at most. Generally a verbal response is discouraged unless the child can easily and consistently name the optotypes. Once confidence in matching is established, move to the test chart.

- For the actual test the child is placed 10 feet (or 20 feet, depending on chart used) from the test chart. The test chart should be 4 to 6 feet from the floor. Proper illumination is critical for accurate and consistent testing.
- Use large optotypes on the test chart to gain the child's confidence.
- Point to the first optotype in each line in descending order.
- Move down until the child hesitates or misidentifies an optotype.
- Move back up one line and ask the child to identify all the optotypes on that line.
- If the child identifies all optotypes correctly go to the next line with smaller optotypes and ask the child to identify all optotypes on the line.
- If the child skips an optotype ask the child to try again while briefly pointing to that optotype.
- A child with an amblyopic eye may typically skip optotype within a line of objects.
- Visual acuity is recorded as the last line on which over 50% (3 of 5, 4 of 6) of the symbols are identified correctly.
- Many lines have less than 6 optotypes making repeating previously shown optotypes necessary.

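### BCVA is summarised as an unadjusted mean change, although baseline BCVA is collected, and separately no common unit is defined for the two charts

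*Combined protocol and SAP*

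**What the plan says.** **Endpoint.** The synopsis and section 2.2 define it as "Mean change in BCVA from baseline over time using either ETDRS or HOTV chart testing depending on age".

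**Analysis.** Section 8.1 is the only analysis text for continuous variables: "Descriptive statistics such as number of observations, mean, median, standard deviation, minimum and maximum will be presented by treatment arms for continuous variables". It adds: "Analysis results will be presented by study drug vs. standard of care topical drops overall and by surgical procedure group". No model, baseline adjustment or confidence interval is planned for any endpoint. The section also states: "This is a feasibility study and the sample size of 30 is not designed to provide power to determine any differences between arms".

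**Design.** Section 4.1 says "Patients in each treatment group (surgery or laser) will be randomized 2:1 at the time of surgery/laser to receive either" the insert or the drops, and "Each treatment group (surgery or laser) will include 15 patients total, 10 receiving Dextenza and 5 receiving the control drug". That makes 20 v 10 overall.

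**Measurement.** Sections 5.1 and 5.2.1 schedule BCVA at Visit 1 and again at Visits 3 to 6. Section 5.2.1 allows either chart at 4 m, with HOTV for children who do not yet read. Tables 1 and 2 name ETDRS only, at 4 m. The HOTV instructions in section 10.2 seat the child at 10 or 20 feet and score by whole line: "Visual acuity is recorded as the last line on which over 50% (3 of 5, 4 of 6) of the symbols are identified correctly". No scoring rule is given for ETDRS, and no reporting unit for either chart.

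**The concern.** There are two separate weaknesses.

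**Baseline.** Eligible eyes (section 4.1.1) range from lattice degeneration to retinal detachment, so starting acuity may vary widely. With 10 controls, some chance difference between arms is to be expected. A change score subtracts the whole baseline value, whereas follow-up acuity tracks baseline only in part. The arm that happens to start worse therefore tends to show the larger gain. Set side by side, two mean changes could suggest that the insert helps or harms vision when part of the gap is regression to the mean.

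**Unit.** One mean is asked for across two charts without a shared scale. From the same records, two analysts could produce different figures: pooled in chart units, pooled after conversion, or split by chart.

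**Working it through.** **1. The plan's own figures.** There is no power calculation to reproduce. The split checks: 15 × 2/3 = 10 and 15 × 1/3 = 5 per procedure group, so 20 and 10 overall.

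**2. Chance baseline difference.** Let s be the SD of BCVA within a procedure group, taken as equal in both groups.
- One group (10 v 5): SE = s√(1/10 + 1/5) = 0.548s.
- Overall: each group supplies half of each arm, so the overall difference is the average of the two. SE = ½√(2 × 0.30) s = 0.387s, the same as s√(1/20 + 1/10).
- Chance of a difference beyond 0.5s (normal approximation): 20% overall, 36% in one group.

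Only within-group spread enters. Acuity differences between surgery and laser eyes are balanced by the 10 v 5 allocation in each.

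**3. Carry-over.** With equal SDs at baseline and follow-up and correlation r, a baseline difference D shifts the expected arm difference in change by −(1 − r)D. For D = 0.5s this is −0.25s (r = 0.5), −0.10s (r = 0.8) or −0.05s (r = 0.9). A simulation of 20,000 trials per value of r, at 20 v 10, gave slopes on D of −0.500, −0.204 and −0.100 for raw change. For the baseline-adjusted difference all slopes were within 0.006 of zero. Averaged over trials, the raw-change difference was within 0.003 SD of zero, so it is unbiased over randomisations.

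**4. Precision, overall comparison (N = 30, units of s).**
- SE of raw change: 0.387√(2(1 − r)).
- SE adjusted: 0.387√((1 − r²)(1 + 1/(N − 4))).
- Variance ratio, adjusted to raw: (1 + r)/2 × 27/26.

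| r (assumed) | SE raw change | SE adjusted | Variance ratio | Reduction |
|---|---|---|---|---|
| 0.5 | 0.387 | 0.342 | 0.779 | 22% |
| 0.8 | 0.245 | 0.237 | 0.935 | 7% |
| 0.9 | 0.173 | 0.172 | 0.987 | 1% |

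Adding procedure group replaces 27/26 by 26/25, which changes the reductions by less than 0.2 percentage points. Within one procedure group (N = 15) the factor is 12/11, giving ratios of 0.818, 0.982 and 1.036: 18% lower, 2% lower and 4% higher.

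**5. Illustration in logMAR.** The documents give no SD. If s were 0.4 to 0.6 logMAR, a one-SE imbalance would be 0.155 to 0.232 (0.4 × 0.387 and 0.6 × 0.387). The part carried over would be:
- r = 0.5: 0.077 to 0.116
- r = 0.8: 0.031 to 0.046
- r = 0.9: 0.015 to 0.023

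Relative to the SE of the raw-change difference this is √((1 − r)/2) = 0.50, 0.32 and 0.22. If much of the spread lies between surgery and laser, s is smaller and the logMAR figures shrink in proportion.

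**6. Chart and distance, side by side.**

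| Place | Chart | Distance |
|---|---|---|
| Section 2.2 | ETDRS or HOTV by age | not given |
| Tables 1 and 2 | ETDRS only | 4 m |
| Section 5.2.1 | ETDRS or HOTV by age | 4 m |
| Section 10.2 | HOTV | 10 or 20 feet (3.05 or 6.10 m) |

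Reading a chart marked for one distance at another, uncorrected, offsets the score by log10 of the ratio: log10(4/3.05) = 0.12 or log10(4/6.10) = −0.18 logMAR. A constant offset cancels in a child's change. A distance that varies between visits does not.

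**The case against.** The strongest reply is that nothing is being tested. Section 8.1 calls this a feasibility study, disclaims power and plans only summary statistics by arm. BCVA is one of nine secondary items, and section 8.1.1 already tabulates selected baseline clinical variables, which could reveal an imbalance (BCVA is not named there). This stands as a limit on importance: no planned test or interval is distorted. It does not dispose of the point, because the stated aim includes efficacy and the arm means will be read against each other.

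The gain may also be slight. At r near 0.9 adjustment saves about 1% of variance overall and may lose a little at 10 v 5. Even at r = 0.5, a one-SE imbalance carries over only half an SE. This stands too, and is why the within-group results are best left descriptive.

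A reader might infer three stronger things that the documents do not support:
- **That the BCVA comparison is biased.** Over randomisations raw change is unbiased. Only a fraction of the imbalance that actually occurs carries over.
- **That the two charts cause the carry-over.** It would arise with one chart, and baseline adjustment does not repair mixed units.
- **That the plan pools raw chart scores.** One mean with no split by chart suggests pooling, but pooling is not stated. Scoring is documented for HOTV only, so a difference in scoring between the charts is not shown.

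**Conclusion.** The concern holds as a minor improvement. The stated summary leaves available baseline information unused. The cost is avoidable imprecision, conditional on the within-group imbalance that occurs: 10% to 50% of it, with reversed sign, for r from 0.9 down to 0.5. Adjustment removes that expected carry-over and lowers the variance of the overall difference by about 1% to 22%.

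These figures rest on an assumed r, equal SDs at baseline and follow-up, and a linear relation. If the SDs differ, the regression slope of follow-up on baseline takes the place of r in the carry-over. The logMAR sizes also rest on an assumed SD.

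The unit problem needs no assumption. No common BCVA unit or ETDRS scoring rule is given, and the chart and distance wording conflicts between sections.

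**What to change.** 1. State in section 8.1 that BCVA from both charts is expressed in logMAR, and give the ETDRS scoring rule. Conversion supplies a common unit, but HOTV values will still move in whole-line steps, which the report should say.
2. Reconcile Tables 1 and 2, section 5.2.1 and section 10.2 on which charts are used and at what distance, and keep chart and distance the same for a child at every visit.
3. Keep the descriptive mean-change table. Beside it, at each follow-up visit, report the overall insert-minus-drops difference with a 95% interval from a linear model with baseline logMAR BCVA and procedure group as covariates, labelled exploratory.
4. Leave the 10 v 5 results within procedure groups descriptive.

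The cost is some wording, one extra model and one or two degrees of freedom. No new data are needed. If r is near 0.9 there is little precision to gain, but the interval still shows how uncertain the comparison is.
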